9.2 AUDITING AND INSPECTING.....	17
10. ETHICAL CONSIDERATIONS.....	17
10.1 RISKS.....	17
10.2 BENEFITS.....	18
10.3 RISK BENEFIT ASSESSMENT.....	18
10.4 INFORMED CONSENT PROCESS / HIPAA AUTHORIZATION.....	18
11. STUDY FINANCES.....	18
11.1 FUNDING SOURCE.....	18
11.2 CONFLICT OF INTEREST.....	18
11.3 SUBJECT STIPENDS OR PAYMENTS	18
12. PUBLICATION PLAN.....	18
13. REFERENCES	19
14. ATTACHMENTS	19

CONFIDENTIAL

This material is the property of the University of Pennsylvania.

Study Summary

Title	Ultrasound to Enhance Treat-to-Target in Rheumatoid Arthritis: A Cross-sectional study
Short Title	Ultrasound Efficacy in Moderate RA
Methodology	Single-arm pilot interventional study
Study Duration	Approximately 12 months
Study Center	Clinic sites for the University of Pennsylvania Division of Rheumatology: Perelman Center for Advanced Medicine (PCAM), Penn Medicine University City (PMUC), Radnor, Valley Forge, and Cherry Hill
Objectives	
Primary:
 
• To determine the frequency of low synovitis scores by ultrasound in patients with RA in moderate or high disease activity with a low number of swollen joints. 
Secondary:
 
• To compare physician treatment recommendations for patients with RA in moderate disease activity before versus after receiving ultrasound results.
Number of Subjects	40
Main Inclusion and Exclusion Criteria	
Inclusion:
 
• Age ≥ 18• Meet ACR 2010 Criteria for RA• Treatment with a DMARD• Clinical Disease Activity Index (CDAI) > 10 (Composite score: Swollen Joint Count (SJC) + Tender Joint Count + Patient Global Score + Physician Global Score)• SJC ≤ 2 
Exclusion:
 
• Evidence of significant large joint activity with warmth and swelling (knee, hip, shoulder, elbow)• Joint MRI or musculoskeletal ultrasound in the past 3 months
Statistical Methodology	
Primary Endpoint Analysis: To assess patient characteristics associated with having low synovitis scores to inform inclusion criteria for a future interventional study. Fisher's exact tests will be used to compare the proportion of low synovitis scores in patients in certain prespecified subgroups.
 
Secondary Endpoint Analysis: The frequency of changes in physician treatment recommendations and disease activity assessment, and provider

CONFIDENTIAL

This material is the property of the University of Pennsylvania.

	confidence in disease activity assessment (5-point Likert scale) before and after ultrasound will be calculated using Fisher's exact tests and Wilcoxon Signed Rank test, respectively.
Data and Safety Monitoring Plan	The PI will be responsible for the data quality management and ongoing safety of the subjects throughout their participation.

CONFIDENTIAL

This material is the property of the University of Pennsylvania.

Background and Study Rationale

This protocol details study procedures that will be conducted in compliance and in full accordance with the provisions set forth in the protocol as well as, Good Clinical Practice standards, all applicable University of Pennsylvania Research Policies and Procedures and all applicable Federal and state laws and regulations. All episodes of noncompliance will be documented and reported accordingly.

1. Introduction

A target-oriented, or “treat-to-target” (T2T), approach for the treatment of Rheumatoid Arthritis (RA) is recommended by the current guidelines. This approach uses more aggressive and expensive therapies. Given the high cost of treatment expenses and the prevalence of RA as a common autoimmune disease, the need for a cost-effective and low medication toxicity approach is needed in order to minimize costs and maximize patient outcomes. In addition to treatment options, routine composite disease activity scores typically do not account for the effect comorbid conditions can have on RA resulting in inaccurate, biased, or elevated scores leading to escalation of therapies such as T2T. Ultrasound has a validated scoring system to grade joint inflammation and might serve as an unbiased and more precise approach to tailoring treatments for patients with moderate disease activity while cutting costs, reducing adverse medication events, and maximizing patient outcomes. This study will recruit 40 eligible patients with RA with moderate or high disease activity to determine if a bilateral hand/wrist ultrasound can inform disease activity assessment.

1.1 Background and Relevant Literature

Rheumatoid arthritis is a common autoimmune disease characterized by joint inflammation and destruction affecting roughly 1% of the population. Supported by several clinical trials, current guidelines recommend a target-oriented approach to the management of RA in which the physician measures and quantifies clinical disease activity and escalates disease modifying anti-rheumatic drug (DMARD) therapy in patients with elevated scores.¹⁻³ This “treat-to-target” (T2T) approach is more aggressive, generally resulting in more treatment changes and greater use of more aggressive and expensive therapies. RA is one of the most expensive conditions to treat and there is a critical need to identify ways to reduce the costs of care and minimize medication toxicity while maintaining excellent patient outcomes.⁴

Significant evidence has emerged that composite disease activity scores are frequently inaccurate or biased. For example, elevations in components of disease activity scores are influenced by factors such as prior joint damage, osteoarthritis, depression, fibromyalgia, obesity, and other comorbid conditions.⁵⁻⁷ In practice, a high proportion of patients are unable to meet definitions of remission or low disease activity. False elevations in disease activity scores can result in inappropriate escalations in therapy that increase costs and expose patients to excess treatment side effects.

Ultrasound has shown promise in objectively measuring disease activity – this modality is less expensive than MRI, has a validated scoring system to grade joint inflammation, and is increasingly widely available, with many rheumatologists now being trained to perform ultrasound at the point of care.⁸ While imaging modalities have been found to perform well as imaging biomarkers of disease activity, large clinical trials found no benefit of incorporating imaging-directed treatment targets among patient in clinical remission.⁹⁻¹¹ Yet a critical knowledge gap remains: whether use of ultrasound in patients with *moderate disease activity* can promote more precise use of therapy, reduce the rate of treatment change, and reduce the cost of care and the rate of adverse medication events while maximizing patient outcomes.

2. Study Objectives

2.1 Primary Objective

To determine the frequency of low synovitis scores by ultrasound in patients with RA in moderate or high disease activity with a low number of swollen joints.

CONFIDENTIAL

2.2 Secondary Objectives

To compare physician treatment recommendations for patients with RA in moderate disease activity before versus after receiving ultrasound results.

3. Investigational Plan

3.1 General Design

This single-arm pilot interventional study will evaluate the potential for ultrasound to improve disease activity assessments for patients with rheumatoid arthritis with clinical scores indicating moderate or high disease activity.

3.2 Allocation to Interventional Group

All eligible and consented participants will receive a bilateral hand/wrist musculoskeletal ultrasound.

3.3 Study Measures

Patient measures:

1. Routine Assessment of Patient Index Data (RAPID3): A pooled index of the 3 patient reported American College of Rheumatology (ACR) RA core data set measures: function, pain, and patient global estimate of status. Each of the 3 individual measures is scored 0 to 10, for a total of 30, and remission was defined as RAPID3 score ≤ 3 . All patients in Penn's rheumatology practice are currently asked to complete the RAPID3 prior to the visit as part of routine patient care. The RAPID3 survey will be used to identify patients more likely to be eligible for the study.
2. Clinical Disease Activity (CDAI): The CDAI is performed by the treating physician at the time of the clinic visit as part of routine care. CDAI is calculated as the sum of swollen joint count (SJC, 0-28), tender joint count (TJC, 0-28), patient global assessment (PGA, 0-10), evaluator global disease activity (EGA, 0-10). Tenderness and swelling are evaluated in the first through fifth metacarpophalangeal joint, the interphalangeal joint of the thumb, the second through fifth proximal interphalangeal joint, the wrists, elbows, shoulders, and knees. The PGA estimate represents the patient's self-assessment of disease activity on a 0-10 scale where 10 means maximal activity. The EGA estimate represents the evaluator's assessment of disease activity on a 0-10 scale where 10 means maximal activity.

CDAI ≤ 2.8 : Remission
CDAI > 2.8 and ≤ 10 : Low Disease Activity
CDAI > 10 and ≤ 22 : Moderate Disease Activity
CDAI > 22 : High Disease Activity

Provider must indicate CDAI >10 and SJC ≤ 2 and no large joint involvement for participant to be eligible.

3. Polysymptomatic Distress Questionnaire (PSD): Combined Widespread Pain Index (WPI), or measure of pain severity extent (0-19 scale) and Symptom Severity scale (SS), or measure of symptom severity (0-12 scale). The PSD scale, 0-31, is an overall

CONFIDENTIAL

This material is the property of the University of Pennsylvania.

measure of pain extent and symptom distress. Used as a diagnostic tool for fibromyalgia by the guidelines set by the 2010 ACR criteria.

4. PROMIS depression, pain, fatigue: Patient-Reported Outcomes Measurement Information System (PROMIS) is a set of person-centered measures that evaluates and can monitor physical, mental, and social health in individuals living with chronic conditions. Short form versions of these measures will be used.
5. C-reactive protein (CRP): Substance secreted by the liver. Routine blood test performed as part of standard clinical care to measure inflammation and assess disease activity in RA.
6. Musculoskeletal ultrasound (see below)

Chart review to obtain additional participant information:

- Demographics: Age, sex, race/ethnicity, BMI, smoking
- Medical History: RA disease duration, RF, CCP, current DMARDs, current glucocorticoid dose, current NSAID use, opioid use, number of previous biologics/JAKi
- Comorbidities: Presence of peripheral joint osteoarthritis, chronic back pain/back osteoarthritis, anxiety, depression, sleep apnea, fibromyalgia

Provider measures:

1. Pre-ultrasound assessment/treatment form:
 - Assessment of the patient's disease activity: providers will select whether they think the patient is in remission, low, moderate, or high disease activity (does not need to match the patient's CDAI score)
 - Confidence in the disease activity assessment (1-10) on a visual analog scale (VAS). A VAS tries to measure a characteristic or attitude that is believed to range across a continuum of values and cannot be easily directly measured.
 - Treatment recommendations: Providers will be asked whether their recommendation for treatment is as follows: no change, increase disease modifying anti-rheumatic drugs (DMARD) dose, or add/switch DMARD.
2. Post-ultrasound assessment/treatment form:
 - Same as the pre-ultrasound form but completed after ultrasound results are reviewed

Musculoskeletal ultrasound assessment

- Bilateral hands/wrists with gray-scale and power doppler (to be performed by the musculoskeletal ultrasound department or by an ultrasound certified rheumatologist within 3 weeks of visit 1. Synovitis in the metacarpophalangeal joint (MCPs), proximal interphalangeal joint (PIPs), and wrists will be graded as absent, mild, moderate, or severe according to the validated OMERACT scoring system. Images will be stored to allow a second reader to score images to assess inter-rater reliability.
 - OMERACT is the acronym for an international, informally organized network initiated in 1992 aimed at improving outcome measurement in rheumatology. Data driven recommendations are prepared and updated by expert working groups. Recommendations include core sets of measures for most of the major rheumatologic conditions
 - Patients in whom all measured joints have absent or mild synovitis will be considered to have low synovitis scores

CONFIDENTIAL

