4.5 Subject Recruitment

Patients scheduled for an upcoming rheumatology appointment at PCAM, PMUC, Radnor, Valley Forge, or Cherry Hill with a rheumatology provider who has opted-in to participate in the study will be pre-screened using EPIC to confirm that they meet criteria for RA, are receiving a DMARD, and are ≥ 18 years old. If providers find that a particular patient might meet the eligibility criteria, they can also refer their patient to the research team.

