5.1 Pre-screening/Screening

Patients with scheduled visits in the rheumatology clinic will be pre-screened for age, RA diagnosis, and DMARD treatment. If patients who are being pre-screened have already completed the RAPID3 survey, the survey score will be assessed for eligibility.

Patients will be contacted through the My Penn Medicine patient portal to inform them about the study and to remind them to complete their RAPID3 survey (sent to all patients in the practice as part of routine care), with the option to opt-out of further pre-screening assessments. Patients without My Penn Medicine or who do not complete the RAPID3 survey will be contacted by phone to inform them about the study and to administer the RAPID3 survey if patients are interested in the study. Patients may still be recruited on the day of their clinic visit, even if a RAPID3 has not been measured or is low, if the patient meets inclusion criteria on the day of the clinic visit.

RAPID3 eligibility criteria:

If RAPID3 ≤ 6 :

- Patients will be informed through MPM and/or phone that they are not likely eligible for the study at this time but might be at a future visit. Providers can still refer these patients to the study and they can be included if they meet inclusion criteria on the day of their office visit.

If RAPID3 > 6 :

- Patients will be informed through MPM and/or phone that they may be eligible for the study depending on their routine exam in clinic.
- Providers will be notified of potentially eligible patients

Providers will perform routine standard of care assessment of disease activity using the CDAI (see 3.3 Study Measures) at the patient's clinic visit. If the score meets the study eligibility criteria, the patient will be approached either at the clinic visit or by phone and asked if they are interested in the study. If they are, the consent process will be conducted.

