5.2 Post-screening Procedures

5.2.1 Visit 1

1. Informed Consent Process / HIPAA Authorization: All subjects for this study will be provided a consent form either in person or electronically describing the study and providing sufficient information for subjects to make an informed decision about their willingness to participate. See

CONFIDENTIAL

Attachment [consent form number] for a copy of the Informed Consent Form. This consent form will be submitted with the protocol for review and approval by the IRB for the study. The formal consent of a subject, using the IRB-approved consent form, must be obtained before that subject undergoes any study procedure. The subject, or legally acceptable surrogate, must sign the consent form in person or electronically, as well as the investigator-designated research professional obtaining the consent. Subjects will be consented by the Clinical Research Coordinator, PI, or Co-Investigator in a private room or by phone followed by electronic signature. Potential subjects will review the consent form in detail with the person designated to consent and have the ability to take the consent home for further review.

2. Patients will complete patient surveys in clinic or will be sent a REDCap link to complete surveys remotely (see 3.3 Study Measures)
3. Physicians will complete the pre-ultrasound assessment (see 3.3 Study measures) in person or will be sent a REDCap link to complete the survey remotely

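### The pre-ultrasound treatment item, as described, cannot tell a settled 'no change' from a decision held back for the study scan

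*Combined protocol and SAP*

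**What the plan says.** The secondary objective (2.2) compares treatment recommendations "before versus after receiving ultrasound results". Sections 3.4.2 and 6.3.2 carry this out by comparing the proportion of patients with escalation recommended (dose increase, or DMARD added or switched) before and after ultrasound, and by counting changes in recommendation.

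The 'before' value comes from the provider's pre-ultrasound form. Section 3.3 describes the item: "Providers will be asked whether their recommendation for treatment is as follows: no change, increase disease modifying anti-rheumatic drugs (DMARD) dose, or add/switch DMARD". The post-ultrasound form repeats the same items once results have been reviewed.

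The order of events is set in 5.2.1. Consent is step 1 and "must be obtained before that subject undergoes any study procedure". Patient surveys are step 2. The provider's form is step 3: "Physicians will complete the pre-ultrasound assessment (see 3.3 Study measures) in person or will be sent a REDCap link to complete the survey remotely".

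The provider knows by then that a scan will follow. Section 3.2 states that "All eligible and consented participants will receive a bilateral hand/wrist musculoskeletal ultrasound". Section 3.3 times the scan, done by the musculoskeletal ultrasound department or "by an ultrasound certified rheumatologist within 3 weeks of visit 1". Section 4.5 recruits from patients "with a rheumatology provider who has opted-in to participate in the study", and 5.1 adds, for patients with a RAPID3 above 6, that "Providers will be notified of potentially eligible patients". The provider also performs the CDAI on which eligibility depends.

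No other baseline is described. The study is single-arm (3.1). The chart review in 3.3 lists current DMARDs, not the plan made at the visit. Section 6.3 deals only with adjustment for confounding.

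**The concern.** The protocol's rationale (1.1) is that falsely raised activity scores lead to inappropriate escalation, and that ultrasound might reduce it. To speak to that, the 'before' answer should be what the provider would recommend with no scan in prospect. A provider who leans towards escalation but expects imaging within three weeks can honestly answer no change for now. That answer is already a consequence of the scan, yet it is stored as the value before it.

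Two misclassifications follow. An escalation that the scan averts is recorded as no change then no change, and drops out of sight. An escalation that was intended all along and goes ahead is recorded as no change then escalate, and is credited to the scan. Nothing described in the protocol would let the analyst recognise either case afterwards. Section 6.1 says the pilot is to support power calculations for later studies, so a distorted estimate would carry forward into them.

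**Working it through.** The plan gives no escalation rates, alpha or power, so there is no stated figure to reproduce. The order of procedures and the provider's awareness are read directly from the sections above. The arithmetic below only shows how sensitive the comparison is. From the documents: 20 evaluable patients and about 40 consented (4.2). Everything else is assumed.

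**Step 1: counts.** Assume 12 of 20 patients would be escalated with no scan in prospect and 8 of 20 are escalated after it. The true change is 8/20 - 12/20 = -20 points. If k of the 12 are deferred and marked no change, recorded 'before' = (12 - k)/20 and recorded change = 8/20 - (12 - k)/20.

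| k deferred | share of the 12 | recorded before | after | recorded change |
|---|---|---|---|---|
| 0 | 0 | 12/20 = 60% | 40% | -20 points |
| 2 | 1/6 | 10/20 = 50% | 40% | -10 points |
| 4 | 1/3 | 8/20 = 40% | 40% | 0 |
| 6 | 1/2 | 6/20 = 30% | 40% | +10 points |

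Each step of 10 points is two patients. The sign reverses only if more than one third of intended escalations are deferred.

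**Step 2: general form.** Let a = share escalated both without and after the scan, b = share escalated without it but not after, c = share escalated only after, and d = share of intended escalations deferred. Assume the post-ultrasound answer is unaffected.

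- Recorded 'escalate then no change' = b(1 - d).
- Recorded 'no change then escalate' = c + ad.
- Recorded change in the escalation rate = (c - b) + d(a + b), which is zero at d = (b - c)/(a + b).
- Recorded frequency of any change between escalation and no change = b + c + d(a - b).

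| Assumed a, b, c | true change | change at d = 20% | zero at | any change, d = 0 then d = 20% |
|---|---|---|---|---|
| 35%, 25%, 5% | -20 | -20 + 0.2 x 60 = -8 | 20/60 = 33% | 30%, 32% |
| 30%, 30%, 5% | -25 | -25 + 0.2 x 60 = -13 | 25/60 = 42% | 35%, 35% |
| 20%, 40%, 5% | -35 | -35 + 0.2 x 60 = -23 | 35/60 = 58% | 45%, 41% |

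In the middle row the frequency of any change does not move at all, while its make-up does: 'escalate then no change' falls from 30% to 24% and 'no change then escalate' rises from 5% to 11%. The simple count of changed decisions would therefore not reveal the problem.

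**Step 3: effect on a test.** For the middle row, using an exact two-sided McNemar test at an assumed alpha of 0.05 (chosen because both answers come from the same patient), 20% deferral lowers power from 32% to 7.5% with 20 patients, and from 74% to 20% with 40.

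**Step 4: the other direction.** Section 1.1 says guidelines recommend escalation when scores are elevated. A provider who knows the answer is being studied might commit to escalation on the form more readily than in practice. If, for illustration, 2 of the other 8 patients (20 - 12) were marked this way with no deferral, recorded 'before' would be 14/20 = 70% and the recorded change 8/20 - 14/20 = -30 points, overstating the true -20.

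**The case against.** The best reply is that the protocol defines its baseline as the recommendation given before results are received, and the form delivers exactly that. The no-scan recommendation is a reasonable target but is not the one written in 2.2. This stands as far as it goes. A reader might infer that the comparison has no valid baseline; the documents do not support that.

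Several further points also stand. The questionnaire is an attachment not available here, so one can say only that the protocol text specifies neither a no-scan frame nor a deferral response, not that the form lacks them. The item asks for a recommendation, not an order, so a provider who is holding an order may still mark an escalation. Section 5.1 allows patients to be approached by phone, and for them the plan may already be settled when consent is sought. The 3 weeks applies to the scan; no deadline is given for sending the result.

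A reader might also infer that the bias is known to run against the effect the study hopes to show. That would be so under deferral, but step 4 shows another awareness effect with the opposite sign, and the documents give no ground for ranking the two.

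Finally, this is a pilot whose stated aim (6.2) is descriptive evidence, and provider awareness is common in unblinded before/after designs. That limits the severity. It does not remove the reason to act, because nothing described would separate deferrals from true no-change decisions afterwards.

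**Conclusion.** The concern holds as a weakness in how the 'before' recommendation is captured. As the protocol describes the item, deferral pending the scan is possible, is not recorded, and would be indistinguishable from a genuine no-change recommendation. If it occurs, it lowers the recorded 'before' escalation rate by the deferred share of that rate: with an intended rate of 60%, 20% deferral moves the before/after difference by 12 points. Whether it occurs, how often, and whether an opposing effect outweighs it cannot be determined from the documents. The illustrative figures rest on assumed escalation and deferral rates and on an unaffected post-ultrasound answer. Only the secondary endpoint is touched; the proportion with low synovitis scores is not. The change is worth making because it is cheap and the information cannot be recovered once providers have seen results.

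**What to change.** In 3.3, word the pre-ultrasound treatment item as: 'What would you recommend at this visit if no ultrasound were going to be available?', keeping the three response options. Name this answer as the 'before' value in 3.4.2 and 6.3.2. Directly after it, add a yes/no item on whether the decision is being held pending the study ultrasound, and report the number held. If the attached questionnaire already does this, bring the wording into 3.3.

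The cost is one reworded item and one added item in REDCap, affecting data capture only. There are three downsides. 'Before' becomes a hypothetical answer for providers who are deferring, though the added item shows how many. The two forms are no longer worded identically, so the sentence in 3.3 that calls them the same needs amending. The hold item could itself suggest deferral, which is why it should follow the treatment item. The rewording does not remove other effects of providers knowing they are studied; those remain a limitation to report. If enrolment has begun, apply the change to remaining participants and state how many answered each wording.

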3.4.2 Secondary Study Endpoints

The frequency of changes in physician treatment recommendations after ultrasound will be calculated. Fisher's exact tests will be used to compare the proportion of patients for whom treatment escalation (dose increase or DMARD add/switch) is recommended before versus after ultrasound. Differences in disease activity assessment before and after ultrasound will also be compared with Fisher's exact tests, and differences in the provider's confidence in disease activity assessment (5-point Likert scale) before and after ultrasound will be compared with the nonparametric Wilcoxon Signed Rank test.

4. Study Population and Duration of Participation

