5.5 Safety Evaluation

All efforts to uphold patient safety will be obtained. Data and privacy protection will be ensured by administering surveys through Penn REDCap. Verbal and written consent will be obtained from potentially eligible or eligible participants before commencement of any study procedures. Staff performing the study ultrasound will have been properly trained. Although the potential for a confidentiality breach does exist, the research team will follow all standard procedures for training, consent, storage, and reporting to minimize potential exposure of patient information.

6. Statistical Plan

CONFIDENTIAL

The number of patients with evidence of synovitis on ultrasound will be tabulated and compared across key measures such as CDAI, depression scores, polysymptomatic distress questionnaire, and PROMIS pain. The analysis will also summarize and tabulate the number of patients for which the ultrasound information changed the decision-making of the clinical provider.

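### The treatment item on both provider forms has no listed response for reducing or stopping a DMARD, or for any other change, so the descriptive count of changed recommendations may be too low

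*Combined protocol and SAP*

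**What the plan says.** Section 3.3 (Provider measures) lists the responses to the treatment item as "no change, increase disease modifying anti-rheumatic drugs (DMARD) dose, or add/switch DMARD". The post-ultrasound form is described as "Same as the pre-ultrasound form but completed after ultrasound results are reviewed", so it carries the same three. The protocol describes no option for reducing or stopping, no 'other' option and no free-text field. It gives no rule for a provider whose recommendation is not listed.

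Three outputs draw on the provider's recommendation:

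- Sections 3.4.2 and 6.3.2 (Aim 2), descriptive: "The frequency of changes in physician treatment recommendations after ultrasound will be calculated".
- The same sections, tested: the proportion of patients for whom "treatment escalation (dose increase or DMARD add/switch) is recommended before versus after ultrasound".
- Section 6 (Statistical Plan), descriptive: "the number of patients for which the ultrasound information changed the decision-making of the clinical provider".

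Only the second is limited to escalation. The other two are worded to cover any change.

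**The concern.** The responses cover standing still and moving up. The motive of the study is over-treatment. Section 1.1 says "False elevations in disease activity scores can result in inappropriate escalations in therapy", and section 3.3 admits only patients with a raised composite score and few swollen joints ("Provider must indicate CDAI >10 and SJC ≤ 2 and no large joint involvement for participant to be eligible"). Some providers may already doubt the score in such patients and choose 'no change' before the scan. For them, the only change that the item can register afterwards is an escalation.

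The form is also uneven within itself. Its disease activity item runs from remission to high and need not agree with the CDAI. A provider can therefore record a lower view of disease activity after a quiet scan, but not a matching lower treatment recommendation.

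At stake is a named secondary endpoint. Section 6.1 says that the pilot is to inform power calculations for later studies, so an under-counted change rate could be carried into their planning.

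**Working it through.** The plan states no expected change rate, effect size or power for this endpoint, so there is no figure to reproduce. The check has two parts.

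**1. Which changes can the form register?**

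Inputs: three possible answers before ultrasound (section 3.3), and four possible true views afterwards (the same three plus reduce/stop). Assumption: a provider who favours a reduction ticks 'no change', the nearest listed answer. The documents do not say this.

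| Before | After: no change | After: increase | After: add/switch | After: reduce/stop |
|---|---|---|---|---|
| no change | same | counted | counted | **lost** |
| increase | counted | same | counted | counted, depth not shown |
| add/switch | counted | counted | same | counted, depth not shown |

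There are 3 × 4 = 12 transitions. Three are unchanged, so 12 − 3 = 9 are true changes. The form registers 8 and loses 1, from 'no change' to reduce/stop.

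The escalation indicator (increase or add/switch, yes or no) is the same in all 12 cells with or without a reduce option, because a reduction and 'no change' both count as no escalation.

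Three smaller gaps lie outside this grid:

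- A provider who already favoured a reduction before the scan could not record that either, so a move from there to 'no change' is hidden.
- A move between adding and switching stays inside one box.
- A change in other treatment, such as glucocorticoid, has no response.

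**2. How large could the loss be?**

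Let *a* be the proportion at 'no change' before ultrasound, and *r* the proportion of those whose provider favours reduce/stop afterwards. Then:

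- Under-count of the change frequency = *a* × *r*.
- Expected patients lost = *N* × *a* × *r*.
- Chance of losing at least one = 1 − (1 − *a* × *r*)^*N*.

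The documents give neither *a* nor *r*, so both are assumptions. *N* is 20 evaluable or 40 consented (section 4.2).

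| *a* | *r* | Under-count (points) | Lost of 20 | Lost of 40 |
|---|---|---|---|---|
| any | 0% | 0 | 0 | 0 |
| 25% | 10% | 2.5 | 0.5 | 1 |
| 50% | 10% | 5 | 1 | 2 |
| 50% | 20% | 10 | 2 | 4 |
| 75% | 30% | 22.5 | 4.5 | 9 |

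At *a* = 50% and *r* = 10%, the chance of losing at least one change is 1 − 0.95^20 = 0.64 for *N* = 20 and 1 − 0.95^40 = 0.87 for *N* = 40.

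**The case against.** The strongest reply is that the form already fits the question. Section 1.1 worries about escalation that should not happen and asks whether ultrasound can lower the rate of treatment change. The expected effect is then a planned escalation that is dropped after a quiet scan. That is a move from 'increase' or 'add/switch' to 'no change', and the form registers it. The tested comparison is defined on escalation, and the response options match that definition. Add and switch are pooled in the endpoint on purpose. Glucocorticoid dose is collected by chart review as a patient characteristic, so its absence from a DMARD item is no inconsistency. Both forms also record the provider's disease activity category and confidence, so a lower assessment is captured even where the treatment answer does not move. Finally, this is a descriptive count in a pilot sized on feasibility and cost.

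Most of this stands, and it limits the point. It does not remove it, because two of the planned outputs are worded as any change in recommendation or decision, and the item as described cannot supply that. A shift in assessed disease activity does not replace a missing treatment answer.

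Two cautions also stand. That a reduction would be ticked as 'no change' is an inference, and the item could be left blank. The study questionnaires are an attachment that is not reproduced. If the actual form has more options, section 3.3 should be brought into line with it.

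**Conclusion.** The point holds in a narrow form. As section 3.3 describes the item, a move from 'no change' to reducing or stopping a DMARD has no listed response. The descriptive change frequency and the section 6 count may therefore be too low. The amount is *a* × *r*. Over the assumed ranges (*a* from 25% to 75%, *r* from 0% to 30%) it runs from 0 to 22.5 points, and the documents do not narrow this.

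A reader might infer more, in three ways that the documents do not support:

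- *That the form cannot record change in the direction the study expects.* It can. Dropping a planned escalation, the main scenario in section 1.1, is counted. Only patients already at 'no change' are exposed to the loss.
- *That the escalation comparison is biased.* It is not affected when a reduction is ticked as 'no change'. A blank answer would be a missing-data matter, for which the documents give no rule.
- *That an assumed rate of unlisted answers applies to every patient.* A rate of 10% to 20% applied to all would give 2 to 4 of 20 or 4 to 8 of 40. With half of the patients at 'no change' (assumption), the same rates lose 1 to 2 of 20 or 2 to 4 of 40.

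**What to change.** On both the pre- and post-ultrasound forms, add the responses 'reduce or stop DMARD' and 'other change (specify)'. Keep the escalation endpoint as defined. State in sections 3.4.2 and 6.3.2 that any move between response options counts as a change. Splitting 'add' from 'switch' is optional, since no planned analysis separates them.

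If the forms are not to be altered, the alternative is to say in sections 3.4.2, 6 and 6.3.2 that the item and both descriptive counts cover escalation decisions only.

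The cost is two extra tick-boxes in REDCap, or three with the split. The downside is a few sparse categories in a sample of 20 to 40. The change affects only what the form can record. It takes no view on whether any patient's treatment should be altered.
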